#### **Hepatic Toxicity**

For bilirubin  $> 1.5 - 3.0 \times \text{ULN}$ , not attributable to underlying disease, reduce the dose of etoposide to  $50 \text{ mg/m}^2$ . For bilirubin  $> 3 - 5 \times \text{ULN}$  reduce the dose of etoposide to  $30 \text{ mg/m}^2$ . For bilirubin  $> 5 \times \text{ULN}$  hold etoposide or hold all treatment if starting the next treatment cycle. When bilirubin resolves to  $\leq 5 \times \text{ULN}$ , treatment can be resumed, with etoposide dose to  $30 \text{ mg/m}^2$ . If bilirubin does not improve to  $\leq 5 \times \text{ULN}$  within 3 weeks of first occurrence, discontinue protocol therapy.

### 5.7.2.1.3 Other Grade 3/4 Non-Hematologic Toxicity

Other non-hematologic Grade 3/4 toxicity should be managed as per local SmPC guidelines and institutional standard practices.

**Table 19. Suggested Guidelines for Carboplatin/Etoposide Dose Delay or Reduction**

Adverse Event	Carboplatin Dose	Etoposide Dose
ANC < 1,500/mm  Day 1 of Cycle	Hold next cycle until ANC ≥ 1,500/mm  .	Hold next cycle until ANC ≥ 1,500/mm  .
Treatment delays of > 7 days due to neutropenia	Implement Dose Reduction 1 for 1 st episode.	Implement Dose Reduction 1 for 1 st episode and Dose Reduction 2 for 2 nd episode.
Grade 3/4 febrile neutropenia with ANC < 500/mm  , requiring IV antibiotics	Implement Dose Reduction 1 for 1 st episode. Initiate Prophylactic G-CSF after 1 st episode.	Implement Dose Reduction 1 for 1 st episode and Dose Reduction 2 for 2 nd episode. Initiate Prophylactic G-CSF after 1 st episode.
Grade 3 nausea, vomiting or Grade 4 vomiting	Hold next cycle until resolution to Grade 1 or better. If more than 2 weeks dose delay is required consult with AbbVie TA MD.	Hold next cycle until resolution to Grade 1 or better. If more than 2 weeks dose delay is required consult with AbbVie TA MD.
Platelets < 100,000/mm  Day 1 of Cycle	Hold next cycle until platelets ≥ 100,000/mm  .	Hold next cycle until platelets ≥ 100,000/mm  .
Grade 4 thrombocytopenia	Implement Dose Reduction 1 for 1 st episode.	Implement Dose Reduction 1 for 1 st episode and Dose Reduction 2 for 2 nd episode.
Bilirubin > 1.5 – 3.0 × ULN	No Change	Reduce dose to 50 mg/m 
Bilirubin > 3 – 5 × ULN	No Change	Reduce dose to 30 mg/m 
Bilirubin > 5 × ULN	Hold if bilirubin does not improve to ≤ 5 × ULN within 3 weeks of first occurrence, discontinue protocol therapy	Hold if bilirubin does not improve to ≤ 5 × ULN within 3 weeks of first occurrence, discontinue protocol therapy
Any other Grade 3/4 toxicity	Per local SmPC/institution guidelines	Per local SmPC/institution guidelines

### Section 6.1.2 Deaths

Last paragraph previously read:

During survival follow-up, deaths attributed to progression of disease under study should be recorded only on the Study Completion/Early Discontinuation eCRF.

**Has been changed to read:**

During survival follow-up, deaths should be recorded on Survival eCRF.

**Section 6.1.3 Lack of Efficacy or Worsening of Disease Under Study**

**Add: new last sentence**

Refer to [Appendix F](#) for listing of events expected with progression of ED SCLC.

**Section 6.1.4 Serious Adverse Events**

**In-text table, "Death of Subject" previously read:**

An event that results in the death of a subject when not related to ED SCLC.

**Has been changed to read:**

An event that results in the death of a subject.

**Section 6.2 Adverse Events Expected Due to SCLC or Progression of SCLC**

**Last paragraph previously read:**

These adverse events may occur alone or in various combinations and are considered expected adverse events in SCLC subjects.

**Has been changed to read:**

These adverse events may occur alone or in various combinations and are considered expected adverse events in SCLC subjects but will not be subject to expedited reporting. These data will be captured as efficacy assessment data only.

**Section 6.3 Adverse Event Severity**

**Last paragraph previously read:**

For all reported serious adverse events that increase in severity, the supplemental CRFs also need to be updated and need to include the new AE serial number.

**Has been changed to read:**

For all reported serious adverse events that increase in severity, the SAE supplemental eCRFs also need to be updated and need to include the new AE serial number.

**Section 6.4 Relationship to Study Drug**

**In-text table previously read:**

Reasonable Possibility	An adverse event where there is evidence to suggest a causal relationship between the study drug and the adverse event.
No Reasonable Possibility	An adverse event where there is no evidence to suggest a causal relationship between the study drug and the adverse event.

**Has been changed to read:**

Reasonable Possibility	After consideration of factors including timing of the event, biologic plausibility, clinical judgment, and potential alternative causes, there is sufficient evidence ( information to suggest a causal relationship ).
No Reasonable Possibility	After consideration of factors including timing of the event, biologic plausibility, clinical judgment and potential alternative causes there is insufficient evidence (information to suggest a causal relationship).

**Section 8.1.1.1 Demographics**

**Previously read:**

All baseline summary statistics and analyses will be based on characteristics obtained prior to the initiation of study drug (or randomization for non-treated subjects). Unless otherwise stated, baseline for a given variable will be defined as the last value for that variable obtained prior to the first dose of study drug.

**Has been changed to read:**

Continuous demographic data (e.g., age, height, and weight) will be summarized with means, standard deviations, medians, and minimum and maximum values. Frequencies and percentages will be computed for categorical data (e.g., sex, race, and performance status).

Smoking history can be defined as current smoker (subject who has smoked within the last 12 months and has more than 100 smoking events [for example, cigarettes] in their lifetime), never smoked (subject with a lifetime smoking history of  $\leq 100$  smoking events [for example, cigarettes] in lifetime) and past smoker (subject who has not smoked in past 12 months and has more than 100 smoking events [for example, cigarettes] in their lifetime).

### **Section 8.1.2.1 Primary Efficacy Endpoint**

#### **Last paragraph previously read:**

Progression-free survival will be defined as the number of days from the date of randomization to the date of earliest disease progression (radiographic progression per RECIST version 1.1 or clinical disease progression) or death. All events of disease progression will be included, regardless of whether the event occurred while the subject was still taking study drug or had previously discontinued study drug. If the subject does not have an event of disease progression nor has the subject died, the subject's data will be censored at the date of the subject's last available disease progression assessment (radiographic or clinical).

#### **Has been changed to read:**

Progression-free survival will be defined as the number of days from the date of randomization to the date of earliest disease progression (radiographic progression per RECIST version 1.1) or death. All events of disease progression will be included, regardless of whether the event occurred while the subject was still taking study drug or had previously discontinued study drug. If the subject does not have an event of disease progression nor has the subject died, the subject's data will be censored at the date of the subject's last available radiographic disease progression assessment.

### **Section 8.1.2.3 Tertiary Efficacy Endpoints**

#### **Subsection Duration of Overall Response**

#### **First sentence previously read:**

Duration of overall response will be defined as the number of days from the date of first response (CR or PR) to the earliest documentation of progressive disease (radiographic or clinical).

#### **Has been changed to read:**

Duration of overall response will be defined as the number of days from the date of first response (CR or PR) to the earliest documentation of radiographic progressive disease.

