**Duration of Overall Response**

Duration of overall response will be defined as the number of days from the date of first response (CR or PR) to the earliest documentation of radiographic progressive disease. If a subject is still responding, then the subject's data will be censored at the date of the subject's last available radiographic disease assessment. For subjects who never experience response, the subject's data will not be included in the analysis.

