#### **Duration of Overall Response**

Duration of overall response will be defined as the number of days from the date of first response (CR or PR) to the earliest documentation of radiographic progressive disease. If a subject is still responding, then the subject's data will be censored at the date of the subject's last available disease assessment (radiographic or clinical). For subjects who never experience response, the subject's data will not be included in the analysis.

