### 10.3 Definition of Efficacy Endpoints

**PFS (progression-free survival):** the number of days from the date of randomization to the date of earliest radiographic disease progression or death provided no radiographic disease progression occurred.

All events of disease progression before the initiation of anti-cancer post-treatment therapy will be included, regardless of whether the event occurred while the subject was still taking study drug or had previously discontinued study drug. However, if a disease progression event occurs immediately after a subject misses two or more consecutive disease progression assessments (e.g., 84 days = 12 weeks if previous tumor scan were prior to or on Week 24 Day 7 (Day 168), 105 days = 15 weeks if previous tumor scan were in between of Week 25 Day 1 and Week 30 Day 7 (Day 210), and 126 days = 18 weeks if previous tumor scan were on or after Week 31 Day 1), then this subject's data will be censored at the last disease progression assessment prior to the missing disease progression assessments, or at randomization if disease progression occurred at the first post-baseline disease assessment. All events of death before the initiation of anti-cancer post-treatment therapy will be included for subjects (whether had post-baseline tumor assessment or not) who had not experienced disease progression, regardless of whether the event occurred while the subject was still taking study drug or had previously discontinued study drug. Similar to disease progression, if a death event occurs immediately after a subject misses two or more consecutive disease progression assessments (length of gap is calculated the same way as disease progression), then this subject's data will be censored at the last tumor assessment before death, or at randomization provided subject did not have any post-baseline disease assessment.

If a subject did not have an event of disease progression nor has the subject died on or prior to the cutoff of PFS analysis, this subject's data will be censored at the date of his/her last disease assessment or randomization date provided subject did not have any post-baseline disease assessment.

**OS (overall survival):** the number of days from the date of randomization to the date of death. All events of death will be included.

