If a subject did not die on or prior to the cutoff of OS analysis, this subject's data will be censored at the date of his/her last known alive date, which is defined as the last date of the last survival follow-up visit, the start date of the last AE, the start date or end date of the last dose of any study drugs, the last lab and vital sign collection date, or the last disease assessment date, whichever occurs the last.

**ORR (objective response rate):** the proportion of randomized subjects with objective response (confirmed) as assessed by the investigator using RECIST version 1.1. Response includes both CR (complete response) and PR (partial response). Confirmation is required to determine objective response. Confirmation rules are described as follows,

Confirmed CR: After the first tumor assessment showing CR, the CR will be considered confirmed if the very next tumor assessment also shows CR (with no other responses in between), and if the duration between the two CRs is greater than or equal to 28 days.

Confirmed PR: After first tumor assessment showing PR, the PR will be considered confirmed if a subsequent tumor assessment also shows CR/PR (irrespective of tumor assessment in between that show stable disease) and if the duration of the first PR and the next CR/PR is greater than or equal to 28 days.

All ITT subjects will be included in the ORR analysis. Subjects with no post-baseline confirmed response will be identified as non-responders. Data after the first appearance of PD, or the start date of any anti-cancer post-treatment therapy, whichever comes earlier, will not be included.

**DOR (duration of overall response):** the number of days from the date of the first confirmed response (CR or PR) to the earliest documentation of radiographic progressive disease or death. The inclusion and exclusion criteria for PD and death, as well as event censoring strategy, are the same as described in PFS endpoint.

If a subject is still responding on or prior to the cutoff of DOR analysis, then the subject's data will be censored at the date of the subject's last available disease assessment.

Subjects with no post-baseline confirmed response will not be included in the DOR analysis. Data after the first appearance of PD, or the start date of any anti-cancer post-treatment therapy, whichever comes earlier, will not be included.

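### Protocol Section 8.1.2.3 ends duration of response only at radiographic progression but censors it at the last radiographic or clinical assessment, contradicting the Synopsis and the parallel PFS rule

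*Protocol*

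**What the plan says.** **Protocol Section 8.1.2.3 (current text).** DOR runs from the first CR or PR "to the earliest documentation of radiographic progressive disease". A subject still responding is "censored at the date of the subject's last available disease assessment (radiographic or clinical").

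**Protocol Synopsis (current text).** The event is the same, but the responder is "censored at the date of the subject's last available radiographic disease assessment".

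**Protocol Section 8.1.2.1, PFS.** The event is radiographic progression or death. A subject without an event is "censored at the date of the subject's last available radiographic disease progression assessment".

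**Protocol Appendix G.** The log is useful only for showing how the mismatch arose. The DOR event in Section 8.1.2.3 formerly ran "to the earliest documentation of progressive disease (radiographic or clinical"), and the amendment rewrote only that first sentence. For PFS it rewrote both the event and the censoring date.

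**SAP Section 10.3.** DOR ends at radiographic progression or death, and its censoring is said to follow the PFS approach. An ongoing responder is "censored at the date of the subject's last available disease assessment". The PFS sentence has a subject without an event "censored at the date of his/her last disease assessment or randomization date" if there was no post-baseline assessment. Neither sentence says *clinical*, and neither says *radiographic*.

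**Role of DOR.** It is tertiary, with a Kaplan-Meier median and confidence interval per arm and no test (Protocol Section 8.1.5.1, SAP Section 10.6.1).

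**The concern.** A censoring date should be the last date on which the subject was known to be free of the event. When the event can be seen only on a scan, that is the last scan. Section 8.1.2.3 allows a later date: a clinical assessment, which cannot produce a DOR event. The interval from the last scan to that date is then counted as response without any scan to support it.

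Two things are at stake. First, the Protocol gives two censoring rules for one endpoint, so the date could be chosen after the data are seen. Second, under the Section 8.1.2.3 rule the reported DOR curve and median can be too high.

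**Working it through.** **1. The texts side by side**

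| Place | Event | Censoring date |
|---|---|---|
| Protocol Synopsis, DOR | radiographic progression | last radiographic assessment |
| Protocol 8.1.2.3, DOR | radiographic progression | last radiographic or clinical assessment |
| Protocol 8.1.2.1, PFS | radiographic progression or death | last radiographic assessment |
| SAP 10.3, DOR | radiographic progression or death | last disease assessment, type not stated |

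The first two rows cannot both be followed.

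**2. Direction**

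At each event time the Kaplan-Meier curve is multiplied by 1 − d/n, with d events among n at risk. Moving m censored responders from before that time to after it changes the factor to 1 − d/(n + m), which is at least as large. The curve can only stay the same or rise. If no event time falls between a subject's last scan and last clinical contact, nothing changes.

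**3. Size**

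The documents give no DOR median, power or censoring fraction, so there is no figure to reproduce.

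Inputs from the documents:
- 60 subjects per arm (Protocol 8.2) and a background response rate of 50% to 70% (Protocol 3.1): 60 × 0.50 = 30 to 60 × 0.70 = 42 responders per arm.
- Scans every 6 weeks to week 30, then every 9 weeks, ±1 week (Protocol 5.3.1.1).
- Median of 5.5 months. This is the control PFS assumption in Protocol 8.2, borrowed here for time to progression among responders.

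Assumptions not in the documents: exponential progression times, first response at week 6, about 11%, 28% or 44% of responders censored, and the time from last scan to last clinical contact.

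With 36 responders, the mean rise in median DOR in days (share of runs with no change in brackets) was:

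| Contact after last scan | 11% censored | 28% censored | 44% censored |
|---|---|---|---|
| 3 weeks | 1.5 (92%) | 5.8 (74%) | 11.2 (58%) |
| 4 weeks | 1.3 (93%) | 5.7 (72%) | 14.3 (54%) |
| 6 weeks | 3.8 (81%) | 10.4 (50%) | 22.9 (25%) |
| 9 weeks | 5.1 (74%) | 18.3 (21%) | 36.1 (4%) |
| 18 weeks | 7.5 (61%) | 32.8 (6%) | 75.3 (0%) |

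The median under scan-only censoring was about 6.2 to 6.5 months. No run gave a fall.

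The lower rows give every censored responder a long gap. When the gap instead varied between subjects, up to 9 weeks, it averaged about 3.5 to 3.7 weeks. The mean rise was then 1.7 to 1.8, 5.4 to 5.7 and 11.2 to 12.3 days at the three censoring levels (30 and 42 responders). With scans exactly on schedule and contact before the next scan, the rise was 0 days in every run.

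These are averages that include the runs with no change. When the median does move, it jumps to another observed event time, so the move in one trial can be larger. At 4 weeks and 28% censored, 5.7 / (1 − 0.72) ≈ 20 days.

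In relative terms, the largest planned-schedule average is 14.3 days on about 6.3 × 30.4 ≈ 191.5 days, or 7.5%. The smallest is zero.

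**The case against.** **The SAP already governs the analysis and drops the clinical wording.** This largely stands. SAP 10.3 ties DOR censoring to the PFS approach. It measures gaps between assessments from the previous tumor scan. SAP 10.1 censors PFS and DOR at a tumor assessment when new systemic therapy starts. The OS rule lists the disease assessment date separately from follow-up visits, adverse events, dosing, laboratory tests and vital signs. On that usage a disease assessment is a scan, so adding *radiographic* to the SAP clarifies it rather than correcting an error. The Protocol's contradiction with itself remains.

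**A reader might infer that PFS censoring also moves later.** The documents do not support this. Protocol 8.1.2.1 is explicit, and the SAP's scan-based vocabulary points the same way. For the primary endpoint this is a matter of clear wording only.

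**Clinical assessments may rarely fall after the last scan.** This also has force. As Table 8 reads, the clinical progression row is marked in one combination-period column, the six-weekly scan column and the Final Visit, not at maintenance Day 1, where ongoing responders mostly are. A subject leaving the study without radiographic progression must also have a Final Visit scan if none was done in the previous 4 weeks (Protocol 5.3.1.1). That scan rule does not cover responders still on study at the 14 September 2018 cutoff (SAP 10.1). The Protocol also does not say which contacts count as a clinical disease assessment for this purpose.

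**A reader might infer a definite inflation of median DOR.** Treating every three-weekly visit as a clinical disease assessment, in samples of 300 responders, gives rises of about 3% to 8% with 26% to 58% censored and about 14% with 63% censored. Table 8 does not schedule such assessments in maintenance, the censoring fractions are not in the documents, and the arms would have about 30 to 42 responders. The lower percentages overlap the range found above, but that range includes zero.

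**Conclusion.** The point holds as a contradiction in current Protocol text. Section 8.1.2.3 pairs a radiographic event with a censoring date that may be clinical, against the Synopsis and the parallel PFS rule. Followed literally, it can credit response time that no scan supports, and any error is upward.

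The consequence is minor. Under the planned scan schedule the median DOR is often unchanged, and the average shift runs from days to about two weeks. Longer average shifts need missed scans together with substantial censoring. These sizes rest on assumed censoring fractions, exponential times and assumed contact dates. The documents show no bias between arms, no effect on the primary endpoint and no affected test.

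**What to change.** In Protocol Section 8.1.2.3, replace the DOR censoring wording with that of the Synopsis, so that "the subject's data will be censored at the date of the subject's last available radiographic disease assessment". As a clarification, insert *radiographic* before the assessment in the DOR and PFS censoring sentences of SAP Section 10.3.

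While those sentences are open, reconcile one neighbouring difference: the SAP counts death as a DOR event and the Protocol definition does not.

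The censoring change amounts to three wording edits. It needs no new data and no programming beyond choosing the scan date as the censoring variable. The wording should be fixed before the blind is broken.

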**Section 8.2 Determination of Sample Size**

**Subsection Phase 2**

**Subsection title previously read:**

Phase 2

**Has been changed to read:**

Phase 2 Randomized Double-Blind

**Section 13.0 Completion of the Study**

**Last paragraph, first sentence previously read:**

The end-of-study is defined as the date of the last subject's last visit.

**Has been changed to read:**

The end-of-study is defined as the date of the last subject's last on-site visit.

**Appendix C. RECIST (Version 1.1) for Tumor Response (PFS)**

**Subsection Methods of Measurement**

**First and second paragraph previously read:**

Conventional CT should be performed with cuts of 5 mm or less in slice thickness contiguously. This applies to tumors of the chest and abdomen. A scale should be incorporated into all radiographic measurements. MRI can be performed if required by local law, but should have sponsor approval.

If prior to enrollment, it is known a subject is not able to undergo CT scans with IV contrast due to allergy or renal insufficiency, the decision as to whether a non-contrast CT or MRI should be used to evaluate the subject at baseline and follow-up should be guided by the tumor type under investigation and the anatomic location of the disease. For subjects who develop contraindications to contrast after baseline contrast CT is done, the decision as to whether non-contrast CT or MRI should be made based upon discussion with the AbbVie medical monitor.

